9.2.4 Study discontinuation

Boehringer Ingelheim reserves the right to discontinue the study overall or at a particular study site at any time for the following reasons:

1. Failure to meet expected enrollment goals overall or at a particular study site
2. Emergence of any methodological, effectiveness, or safety information that could significantly affect continuation of the study, or any other relevant administrative reasons.
3. Violation of Good Pharmacoepidemiology Practice (GPP), the study protocol, or the contract by a study site, investigator or research collaborator, disturbing the appropriate conduct of the study

The investigator/the study site/research collaborator will be reimbursed for reasonable expenses incurred in case of study/site termination (except in case of the third reason).

9.3 VARIABLES

9.3.1 Exposures

Primary exposure (see Statistical and Epidemiological Analysis Plan for applicable drug codes):

- Main comparison:
 - Incident prescription order of empagliflozin [ATC codes: A10BK03, A10BD20] without prior use of any SGLT2i or DPP4 inhibitors
 - Incident prescription order of any DPP4 inhibitor without prior use of any DPP4 inhibitor or any SGLT2i
- Secondary comparison:
 - Incident prescription order of any SGLT2i without prior use of SGLT2i or GLP1RA
 - Incident prescription order of any GLP1RA without prior use of any GLP1RA or SGLT2i

A modified As-Treated (AT) approach will be used for all analyses. Patients will be included in their incident prescription cohort with censoring occurring for the following reasons:

- Occurrence of outcome of interest
- Empagliflozin user has new prescription for a different SGLT2i during follow-up
- Empagliflozin [SGLT2i] user has new prescription for the comparator drug of interest during follow-up
- DPP4i or GLP1RA user has new prescription for any SGLT2i during follow-up
- No additional prescription for the incident drug has been written in the 1 year (+30 days) since the last observed prescription
- 2 years following index prescription
- End of study period

This modified approach will be used due to inconsistencies in the available prescribing data (e.g., number of fills, number of pills) and discontinuation dates across PCORnet healthcare sites and the fact that claims/fill data are not available in PCORnet to supplement the written orders. We will assume a patient is on their initial prescription unless the criteria above have been met.

To better understand potential limitations of this modified AT approach, a feasibility assessment will be performed once the initial data queries are performed to examine the extent of more detailed prescribing information (e.g., number of fills, number of pills, discontinuation dates) across participating healthcare sites. If feasibility is determined by the investigative team, sensitivity analyses will be performed including sites with more complete prescribing information examining all primary and secondary outcomes (See [section 9.7.2](#)).

The intention-to-treat (ITT) approach will be used as a sensitivity analysis for the primary and secondary comparisons of the primary outcome. In this ITT analysis, follow-up will not be censored when a patient switches to, or adds, treatment with a different agent.

Primary subgroup of interest: diabetic kidney disease (DKD)

- DKD will be defined using diagnosis codes and laboratory values based on records at the index encounter and from other health system encounters up to 12 months prior to index prescription. Analyses will be performed overall and within subgroups of DKD (DKD and no DKD at baseline).

9.3.2 Outcomes

Any outcome requiring at least 2 measurements meeting the event definition over a specified timeframe will have a date of event set to the date of the first measurement.

9.3.2.1 Primary renal effectiveness outcomes

Table 2 Primary outcome included in this study

Outcome	Definition
Composite outcome including 40% decline in eGFR Incident end-stage renal disease (ESRD) All-cause death	40% decline in eGFR: at least 2 measurements* during follow-up of at least a 40% decline relative to baseline separated by ≥ 28 days [R21-4243]. ESKD definition: at least 1 kidney transplant or ESKD diagnosis/procedure ¹ or at least 2 dialysis diagnoses/procedures ¹ separated by ≥ 28 days or eGFR<15 on 2 measurements separated by ≥ 28 days *The second eGFR measurement is required to be within 2 years from index, at which time, all patients will be censored (See Section

9.3.2.2 Secondary outcomes

Table 3 Secondary outcomes included in this study

Outcomes	Definition ¹
Secondary Renal Effectiveness Outcomes	
Secondary outcome 1: 40% decline in eGFR	Same as that used for the primary composite outcome
Secondary outcome 2: Incident end-stage kidney disease (ESKD)	As for ESRD definition from primary composite outcome
Secondary outcome 3: Dialysis	Incident dialysis, given dialysis in the 12 months preceding index date is a disqualifying diagnosis/procedure
Secondary outcome 4: Kidney transplant	Any procedure ¹ associated with healthcare encounters, including hospitalizations and specialist outpatient and primary care encounters
Secondary CV Effectiveness Outcomes	
Secondary outcome 5: Composite outcome including Hospitalization for heart failure All-cause death	Any diagnosis ¹ of heart failure associated with hospital admission, including inpatient and ED to inpatient encounters. From death records provided by sites, supplemented with linkage using Datavant Software.

Outcomes	Definition ¹
Secondary outcome 6: Hospitalization for heart failure	Any diagnosis ¹ associated with hospital admission, including inpatient and emergency department (ED) to inpatient encounters
Secondary outcome 7: All-cause death	From death records provided by sites, supplemented with linkage using Datavant Software.
Secondary outcome 8: Composite outcome including MI ² Stroke ² All-cause death Coronary revascularization procedure	For MI and stroke, any inpatient diagnosis ² associated with healthcare encounters, including inpatient and ED to inpatient For all-cause death, as for secondary outcome 7
Secondary outcome 9: Composite outcome including MI ² Stroke ² All-cause death	For MI and stroke, any inpatient diagnosis ² associated with healthcare encounters, including inpatient and ED to inpatient For all-cause death, as for secondary outcome 7
Secondary safety outcomes	
Secondary outcome 10: Diabetic ketoacidosis	Any diagnosis ¹ associated with healthcare encounters in the inpatient setting
Secondary outcome 11: Severe hypoglycemia	Any diagnosis ¹ associated with healthcare encounters in the inpatient or ED setting
Secondary outcome 12: Urinary tract cancer	Two or more diagnoses ¹ associated with healthcare encounters within 2 months
Secondary outcome 13: Severe Urinary Tract Infections (UTI)	Any diagnosis ¹ associated with healthcare encounters in the inpatient or ED setting for: Pyelonephritis (ICD-10 codes in Annex Table 5-6) Urosepsis. Combination of diagnosis code for UTI and a diagnosis code for sepsis within 1 week (ICD-10 codes for sepsis in Annex Table 5-6, ICD-10 codes for UTI in Annex Table 5-8). In order to rule out nosocomial infection, at least one of the following criteria will have

Outcomes	Definition¹
	to be present within 7 days prior to the hospital admission: Prescription for an antimicrobial agent Outpatient visit with a recorded diagnosis code for UTI or pyelonephritis Outpatient visit with a recorded diagnosis code for UTI or pyelonephritis
Secondary outcome 14: Acute kidney injury that requires dialysis	Any diagnosis ¹ associated with inpatient healthcare encounters for AKI plus at least one inpatient encounter indicating dialysis within 28 days of the AKI encounter Two or more dialysis encounters separated by 28 days or more will be excluded from this definition
Secondary outcome 15: Genital Mycotic infection	Any diagnosis associated with healthcare encounters, including hospitalizations and outpatient encounters, or prescription for fluconazole

1 Detailed variable definitions for the outcomes will be defined based on ICD diagnosis and procedure codes and CPT codes;

2 As heart failure, MI and stroke are defined from diagnosis without mortality data, the outcomes include both fatal and non-fatal events.

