9.2.2.2 Exclusion criteria

Exclusion criteria:

- Aged < 18 years on the first prescription date of the qualifying prescription,
- Pre-existing diagnosis of T1DM during the 12 months before the index date,
- Having a disqualifying diagnosis during the 12 months before the index date, defined as having at least one of the following: eGFR < 30 , dialysis, polycystic kidney disease or a kidney transplant,
- < 12 months of available data before the index date, and/or no complete history of drug dispensations/other records of drug use during this period, defined as not having at least 1 ambulatory visit and at least 1 medication prescription during the preceding 12 months, and
- Missing or ambiguous data on serum creatinine in the 12 months prior to the index date or sex.

[figure not shown]

Figure 1 Consort diagram of study population, the application of inclusion and exclusion criteria, and the resulting study cohorts

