9.7.2.3 Determine the effect of empagliflozin compared to DPP4i on outcomes

Analysis: The effect of empagliflozin compared to DPP4i on outcomes will be assessed using Cox proportional hazards models in a 2-arm comparison. The analysis will include all patients with a valid overlap weight and will be done for overall and within DKD subgroups. The main analysis will assess outcomes while patients remain on initial treatment.

Follow-up will start the day after the index date (date of initiation of empagliflozin or DPP4i) and will continue until the first occurrence of the outcome of interest, or end of study date (date of death, date of study end, 2 years after index date). For the main AT analysis, follow up will be censored early if an empagliflozin user starts a DPP4i or other type of SGLT2i, or if a DPP4i user starts any SGLT2i. For the AT analysis, if an empagliflozin or DPP4i user initiates a GLP1RA, this will be adjusted for in the model using a time-dependent indicator

variable. Additionally, follow-up will be censored early if there is no indication of a new prescription in the year (+30 days) following the last observed prescription.

Incidence rates will be computed as the number of first events per 100 patient years of follow-up. Analyses of time to first event will be performed using Cox proportional hazards models. Outcomes where death is a competing risk will be analyzed using cause-specific proportional hazards models, achieved by censoring follow-up at the time of death. All analyses will be adjusted for covariates (variables) that continue to be unbalanced after reweighting, with any additional covariates that might be of medical interest identified by the clinicians. Hazard ratios comparing empagliflozin to DPP4i with 95% confidence intervals and the adjusted two-sided p-values for superiority testing will be presented for all outcomes.

Kaplan-Meier curves will be created for each outcome in the overall and DKD subgroups using the reweighted population. Kaplan-Meier curves will also be generated to summarize the cumulative incidence of treatment switching by comparator arm.

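### Secondary outcome 12 (urinary tract cancer) does not exclude cancer present before index, so existing cases can be counted as events and bias this safety hazard ratio

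*Protocol*

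**What the plan says.** Protocol Section 9.3.2.2, Table 3, gives the whole rule for outcome 12 as two or more diagnoses "associated with healthcare encounters within 2 months". The natural reading is that the two diagnoses lie within 2 months of each other, at any time in a follow-up of up to 24 months. The row does not require the cancer to be new.

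The disqualifying conditions in Section 9.2.2.2 are renal only: "eGFR < 30 , dialysis, polycystic kidney disease or a kidney transplant". The abstract lists the same conditions.

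Section 9.7.2.3 fixes the risk period and the count: "Follow-up will start the day after the index date", and "Incidence rates will be computed as the number of first events per 100 patient years of follow-up". Section 9.3.2 says that an outcome needing two measurements "will have a date of event set to the date of the first measurement". That sentence speaks of measurements; applied to diagnoses, it would date the event at the first code of the pair.

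The dialysis row of Table 3 does say why it captures new events: "Incident dialysis, given dialysis in the 12 months preceding index date is a disqualifying diagnosis/procedure". The cancer row has no counterpart.

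**The concern.** Cancer is a lasting condition that is coded again at later visits. A patient with bladder or kidney cancer before index stays in the risk set, and two visits coded within 2 months of each other make that patient an event, possibly soon after index. The event is first only in the sense of first since index.

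New urinary tract cancers over at most 2 years are likely to be few, so even a small group of existing cases can form a large part of the count. The hazard ratio then mixes the effect on new cancer with the distribution of old cancer. For a safety outcome this matters in both directions: a real excess can be masked, or an apparent excess can arise where there is none.

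Weighting does not cure this. Balancing cancer history between arms leaves the existing cases in both numerators. The abstract's list of propensity score covariates names heart failure, cardiovascular events and hypertension as comorbidities. It does not name cancer history, although the list is open-ended and the full one is in the SEAP.

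**Working it through.** **Plan's own figure.** The protocol gives no rate, event count or power for urinary tract cancer. Its only sizing figure is for the primary renal composite: 7,593 per group in Table 4, rounded to 7,600, for a hazard ratio of 0.80 and 30 events per 1,000 patient-years. Recalculation with 12 months' accrual and 12 months' further follow-up gives 7,795 per group (Lakatos, monthly steps), 7,957 (Schoenfeld) and 8,020 (Freedman), which is 3 to 6% higher. That is close and does not bear on this point. The size is used below only to turn rates into counts; it cancels from the apparent hazard ratio.

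**Inputs from the protocol (Section 9.5).** N = 7,600 per arm; follow-up 1.5 years (median 18 months).

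**Assumptions, not from the documents.** Reference incidence λ = 0.5, 1 or 2 per 1,000 patient-years; prevalence at index p = 0.2, 0.5 or 1.0%; capture c = 0.5 (half of existing cases obtain two codes within 2 months during follow-up); true hazard ratio 1.5.

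**Formulas**
- New events, DPP4i arm: N(1 − p) × λ × 1.5
- New events, empagliflozin arm: the same × 1.5 (the true hazard ratio)
- Existing cases counted, each arm: N × p × c
- Apparent hazard ratio ≈ (new + existing, empagliflozin) / (new + existing, DPP4i)

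**Worked cell, λ = 1 per 1,000, p = 0.5%**
- DPP4i: 7,600 × 0.995 × 0.001 × 1.5 = 11.3 new
- Empagliflozin: 11.3 × 1.5 = 17.0 new
- Existing: 7,600 × 0.005 × 0.5 = 19.0 per arm
- Apparent hazard ratio: (17.0 + 19.0) / (11.3 + 19.0) = 36.0 / 30.3 = 1.19
- Share of events that are existing cases: 38.0 / 66.3 = 57%

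**Balanced arms: apparent hazard ratio (share of events that are existing cases)**

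| Incidence per 1,000 PY | p = 0.2% | p = 0.5% | p = 1.0% |
|---|---|---|---|
| 0.5 | 1.21 (52%) | 1.11 (73%) | 1.06 (84%) |
| 1 | 1.30 (35%) | 1.19 (57%) | 1.11 (73%) |
| 2 | 1.37 (21%) | 1.27 (40%) | 1.19 (57%) |

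With existing cases excluded, every cell returns 1.50.

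**Unbalanced arms (λ = 1 per 1,000, c = 0.5)**

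| True HR | Prevalence, empagliflozin | Prevalence, DPP4i | Apparent HR |
|---|---|---|---|
| 1.5 | 0.4% | 0.6% | 0.94 |
| 1.5 | 0.6% | 0.4% | 1.50 |
| 1.5 | 0.7% | 0.3% | 1.91 |
| 1.0 | 0.4% | 0.6% | 0.78 |
| 1.0 | 0.6% | 0.4% | 1.29 |

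First row: (17.0 + 15.2) / (11.3 + 22.8) = 32.2 / 34.1 = 0.94. A difference of 0.2 percentage points in residual prevalence is enough to reverse the direction.

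**The case against.** **The SEAP may deal with it.** Table 3's first footnote defers detailed outcome definitions to diagnosis and procedure codes, and the covariate list is in the SEAP. A reader might infer that the study has no washout anywhere; the protocol alone cannot show that. What stands is narrower. The footnote defers codes and names no washout, while Table 3 does state such conditions for other outcomes: a rule against nosocomial infection for urinary tract infection, and exclusion of repeated dialysis for acute kidney injury. The rule as written admits existing cases.

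**The dialysis contrast is limited.** That row reports the effect of a cohort-wide renal exclusion; it does not set an outcome-specific look-back that was then forgotten for cancer. This is fair. The contrast shows only that the question was considered for one outcome and left open for the other.

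**Not every existing case counts.** Visits more than 2 months apart do not qualify, and whether personal-history codes count depends on the codelist. This stands, and it is why half capture is assumed rather than full capture.

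**Dilution is not certain.** A reader might infer that the hazard ratio must move towards 1 and hide a harm. That follows only if existing cancer is balanced between the weighted arms, which the protocol does not establish.

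**The outcome is weak even when repaired.** At 7,600 per arm and 1 new case per 1,000 patient-years, about 11.4 + 17.1 = 28.5 events are expected at a true hazard ratio of 1.5. Schoenfeld's formula gives ln(1.5) × √(28.5/4) − 1.96 = 1.08 − 1.96 = −0.88, or about 19% power. This is true at the planned size, and a larger cohort would have more. Low power is no reason to report a biased estimate and interval.

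**Conclusion.** The point holds for the protocol's stated definition. Outcome 12 can count urinary tract cancer that was present before index, and nothing in the outcome row or the eligibility criteria prevents it. The same definition serves the SGLT2i versus GLP1RA comparison.

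The size is illustrative. It rests wholly on assumed incidence, prevalence and capture: with balanced arms, a true hazard ratio of 1.5 appears as about 1.06 to 1.37, and existing cases make up 21 to 84% of events. Without balance, the direction is not determined. The documents do not support a firm figure, nor a claim that a harm will be hidden.

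A reader might also take the 2 months as the first 2 months of follow-up. The plain sense is the spacing of the two codes, so exposure to this problem runs through the whole risk period.

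This is a secondary safety outcome and the primary renal analysis is untouched. The correction is still worth making, because following the written rule gives an estimate that does not isolate new cancer.

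**What to change.** For outcome 12 only, state in Table 3 that:
- the risk set is limited to patients with no urinary tract cancer diagnosis in the protocol's uniform 12-month look-back, which by the abstract includes the index date;
- the event is the first qualifying pair of codes with both codes after index;
- the analysis is repeated as a sensitivity analysis, excluding patients with such a diagnosis at any time in the available pre-index history.

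The 12-month rule should be the base. Data start in January 2014 and index dates run from 2015 to 2020, so available history ranges from about 1 to 7 years. A rule using all of it would make exclusion depend on the calendar year of initiation, which may differ between arms.

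The cohort for every other outcome stays as it is. If the SEAP already applies a washout, Table 3 needs only to be aligned with it.

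The cost is a line of text and one filter. A few patients leave this outcome's risk set, its event count falls, and a 12-month look-back may miss some older cancers, which the sensitivity analysis helps to gauge.

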9.3.3 Covariates

The overall list of covariates being examined in this investigation is provided in the study SEAP. The SEAP provides an overview of the variables that will either be included in the propensity score modeling for patient matching or presented in descriptive analyses for the baseline variables but will not be included in PS modeling.

9.4 DATA SOURCES

This study will utilize high-quality renal function laboratory data available in medical electronic health records from approximately 20 health systems in the US that have mapped their data to the PCORnet CDM. Sites meeting PCORnet data curation quality checks will be eligible to participate in this study. Sites will be approached for participation in this study based on an initial feasibility assessment to determine the extent and completeness of key data elements (renal laboratory data, prescription data, relevant medical diagnoses, and data from both inpatient and outpatient encounters). Death data will be ascertained from site records and augmented with de-identified encrypted linkage to external sources, which includes reported deaths from the government and commercial obituaries using Datavant Software.

9.5 STUDY SIZE

The estimated required sample size for the primary analysis depends on the incidence rate of the primary composite renal outcome in the reference cohort, and the difference in effectiveness of comparison drugs (hazard ratio, HR) (Table 4). Incidence rates ranging from 13 per 1,000 patient years to 46 per 1,000 patient years (DAPA-CKD SGLT2i cohort) [R21-1080] were considered as representative of anticipated incidence rates in the non-DKD and DKD subgroups. Sample size was estimated to achieve 80% power for a two-sided log rank test with type 1 error of 0.05. Calculations assumed 12 months accrual and 12 months additional follow-up, for a median follow-up of 18 months. Assuming an incidence rate of 30 per 1,000 patient years in the overall cohort, a sample size of approximately N=7,600 per group is estimated to have 80% power to detect a hazard ratio of 0.80. For a subgroup with a higher incidence rate (e.g., 46 per 1,000 patient years), similar power could be achieved with an approximate sample size of N=5,000 per group.

Table 4 Sample size per group, as a function of incidence rate of primary renal outcome and hazard ratio

	Hazard Ratio					
Reference Group Incidence Rate*	0.60	0.65	0.70	0.75	0.80	0.85
13	3843	5178	7264	10771	17316	31648
30	1682	2268	3183	4721	7593	13883
46	1108	1494	2097	3112	5007	9158

* Assumed hazard rate (per 1,000 patient years) in reference cohort

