
 No observed prescriptions for the index drug within 1 year (+30 days) from the last observed prescription 
The primary analysis will be performed using overlap weighting to balance covariates across the two treatment arms (empagliflozin vs DPP4i) and Cox proportional hazards modelling to determine the effect of drug on outcomes. To create the overlap weights, the following will be performed:
 
For each two-arm study comparison and within the DKD and non-DKD subgroups separately, propensity score models will be built using a logistic LASSO model with the covariates of interest and all subgroup by covariate pairwise interactions. The outcome of interest is treatment group, with empagliflozin [or any SGT2i] as the treatment of interest and DPP4i [or GLP1RA] as the reference group. The variables/interactions that are remaining in the LASSO model are refit to a standard logistic regression and the resulting predicted probability for each patient is considered the PS. For patients on the reference treatment, the overlap weight is the same as the PS. For patients on the treatment of interest, the overlap weight is 1-PS. No trimming is required due to the PS weights being bounded between 0 and 1. Distributions of covariates in the DKD and non- DKD groups and further within subgroups of interest will be assessed using standardized mean differences. Absolute standardized mean differences will be visually depicted using the CONNECT-S plot.
 
For each outcome, incidence rates (number of events per 1000 PY of follow-up), hazard ratios, and corresponding 95% confidence intervals (CI) will be presented. Hazard ratios and CI will be calculated using weighted Cox proportional hazards models. For the AT analysis, if an empagliflozin or DPP4i user initiates a GLP1RA during the follow-up period, this will be adjusted for in the comparison of empagliflozin and DPP4i (and similarly for users initiating a DPP4i).
 
Analyses will be performed overall and within DKD subgroups. A sensitivity analysis will be performed using propensity score
			

Proprietary confidential information © 2023 Boehringer Ingelheim International GmbH or one or more of its affiliated companies

Name of company: Boehringer Ingelheim			
Name of finished medicinal product: Jardiance®			
Name of active ingredient: A10BK03 Empagliflozin			
Protocol date: 26 May 2023	Study number: 1245-0228	Version/Revision: 2.0	Version/Revision date: 26 May 2023

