9. RESEARCH METHODS

9.1 STUDY DESIGN

This will be a non-interventional comparative effectiveness and safety study, using existing (secondary) data from up to 20 US health systems that have mapped their electronic health record data to the PCORnet Common Data Model (CDM). The study period will be 1 January 2014 through 31 December 2021, which includes data during the COVID-19 pandemic. There will be an assessment of COVID-era data for quality purposes, and we will perform a sensitivity analysis excluding all data available from March 2020 to the end of the study period.

The primary objective of the study will include patients with T2D who initiate use of empagliflozin or DPP4i without prior use of either drug [class]. The primary analysis will compare patients with T2D initiating empagliflozin to patients with T2D initiating DPP4i.

The secondary objective of the study will include an additional cohort of patients: those with T2D who initiate use of any SGLT2i or GLP1RA without prior use of either drug class.

Propensity score weighting (overlap weighting [[R20-1964](#), [R21-4495](#)]) will be used to balance covariates between two treatment groups in each comparison (empagliflozin vs DPP4i; SGLT2i vs GLP1RA). With overlap weighting, the resulting reweighted sample targets the subpopulation of patients with the most overlap in covariates across the two treatment groups. Patients in this subpopulation have substantial probability to be assigned to either treatment of interest, and therefore represent patients for whom there is clinical equipoise for treatment assignment. Propensity score models will be developed, and the reweighted populations will be assessed to ensure cross-treatment group covariate balance within both the DKD and non-DKD subgroups, as well as for the overall cohorts using methods of Yang et al [[R21-4497](#)]. Additional details about propensity score modeling and reweighting are provided in the section on Data Analysis.

Study feasibility will be evaluated after data collection has occurred. If the final sample size does not meet the required sample size for 80% power, the planned sensitivity and subgroup analyses will be removed from the final study report. The primary analyses will still be assessed but in an exploratory capacity.

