9.7.1 Phased Implementation of Analyses

A phased approach to implementation of data analyses will be used to allow examination of key aspects of the patient populations by treatment group and the prescribing practices by treatment type (i.e., empagliflozin, any SGLT2i, DPP4i and (if feasible) GLP1RA). A first phase of the analyses will focus on descriptive evaluation of differences in demographic and clinical patient characteristics, number and timing of prescriptions across treatment groups, and summary of outcome event rates aggregated across treatment arms. The main rationale for this phased analytic approach is to examine the potential for exposure misclassification due to the limited medication exposure data available in PCORnet (e.g., no pharmacy claims data). Secondary goals of the initial phase will be to assess the degree to which patient characteristics have been well balanced after propensity score weighting, and to confirm that the study will have adequate statistical power based on observed sample size and aggregate event rates for key outcomes. Results from this first analytic phase will be examined and discussed by members of the study team (BI and [REDACTED]) prior to implementation of comparative outcome analysis to provide an opportunity for modification of the study protocol (if needed) and/or study discontinuation if determined appropriate. Additional details for the phased analytic approach, along with codelists and table shells, are provided in the SEAP.

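### The 7,600 per group (5,000 in the higher-rate subgroup) is sized for an unweighted log-rank test, makes no allowance for overlap weighting, and can let the power check pass wrongly in a cohort only modestly above it

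*Protocol*

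**What the plan says.** Section 9.5 of the protocol sets the required size for the primary analysis. The test is fixed in one sentence: "Sample size was estimated to achieve 80% power for a two-sided log rank test with type 1 error of 0.05". The timing is given as "Calculations assumed 12 months accrual and 12 months additional follow-up, for a median follow-up of 18 months". The reference rate for all patients together is taken as 30 events per 1,000 patient-years, and from these inputs the section concludes that "a sample size of approximately N=7,600 per group is estimated to have 80% power to detect a hazard ratio of 0.80". For a subgroup at 46 per 1,000 patient-years it gives about 5,000 per group. Table 4 ("Sample size per group, as a function of incidence rate of primary renal outcome and hazard ratio") prints a single N per group in each cell, 7,593 and 5,007 for these two cases. The Abstract repeats the 7,600 and the 80%. None of these places has a term for weighting.

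The Abstract describes the analysis differently: "The primary analysis will be performed using overlap weighting to balance covariates across the two treatment arms". It takes hazard ratios from weighted Cox models. Section 9.7.2.2 sets the weights: 1-PS for a patient on the treatment of interest and PS for a patient on the reference drug, built separately in the DKD and non-DKD groups.

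Two places then use the required size. Section 9.1 begins its rule with "If the final sample size does not meet the required sample size for 80% power"; in that event sensitivity and subgroup analyses are dropped and the primary analyses become exploratory. Section 9.7.1 asks Phase 1 to "confirm that the study will have adequate statistical power based on observed sample size and aggregate event rates for key outcomes", with protocol modification or discontinuation as possible outcomes.

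**The concern.** An N that gives 80% power for an unweighted comparison does not give 80% for a weighted one. Overlap weights favour patients who could have received either drug and give little weight to those with extreme propensity scores. Each arm then carries the information of its effective sample size, (sum w)^2 / sum w^2, which is below the head count whenever the weights differ.

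The figure has consequences, because section 9.1 uses it to separate a fully reported study from an exploratory one. If head count is compared with an unweighted requirement, a cohort just over the line is treated as adequately powered when its weighted analysis is not, and a null result may be read as stronger evidence than it is. The same applies to the 5,000 quoted for the higher-rate subgroup, since the weights are built within DKD strata.

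**Working it through.** **Inputs from section 9.5.** Two-sided alpha 0.05, power 80%, HR 0.80, reference hazard 0.030 per year (so 0.024 in the other arm), 12 months' accrual plus 12 months' follow-up, one N per group (1:1).

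**Step 1: reproduce 7,593.** With uniform accrual over one year and one further year of follow-up, the event probability is p = 1 - (exp(-λ) - exp(-2λ))/λ, giving 0.04397 for λ = 0.030 and 0.03534 for λ = 0.024.
- Closed form: required events = 4(1.960 + 0.842)^2 / (ln 0.80)^2 = 630.5, and N = 630.5 / (0.04397 + 0.03534) = 7,951 per group, 4.7% above the printed cell. At 7,600 per group, expected events are 334 + 269 = 603 and power is 78.2%.
- A discrete-time log-rank calculation gives 7,588 with 6 intervals per year and 7,795 with 12. On either grid all 18 cells of Table 4 reproduce within 3%.

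The table is therefore correct for an unweighted 1:1 log-rank test, and leaves no margin for anything else.

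**Step 2: information kept under overlap weighting.** With 1:1 groups and a propensity score e distributed symmetrically about 0.5, (sum w)^2 / sum w^2 in each arm equals the head count times RE = 4·E[e(1-e)]. RE is 1 only if e = 0.5 for everyone, so the direction of the loss needs no further assumption.

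**Step 3: size.** The protocol gives no propensity-score distribution. Assumption: logit(e) is normal with mean 0 and SD s, groups are 1:1, follow-up is as in 9.5, and the weights are unrelated to outcome risk. Taking the protocol's 80% at 7,600 as the anchor, power = Φ(2.802·√RE - 1.960), and the head count needed for 80% is 7,600/RE. At s = 1.0, for example, 2.802 × √0.8265 - 1.960 = 0.587, which is 72%.

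| s | c-statistic | RE | Effective N at 7,600 | Power | N per group for 80% |
|---|---|---|---|---|---|
| 0.50 | 0.63 | 0.944 | 7,176 | 78% | 8,049 |
| 0.75 | 0.69 | 0.888 | 6,751 | 75% | 8,556 |
| 1.00 | 0.74 | 0.827 | 6,281 | 72% | 9,196 |
| 1.25 | 0.78 | 0.765 | 5,814 | 69% | 9,935 |
| 1.50 | 0.81 | 0.707 | 5,373 | 65% | 10,751 |

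Starting from the closed-form 78.2% instead of 80% lowers each power by 1 to 2 points. For the higher-rate subgroup, 5,007/RE runs from about 5,300 (c = 0.63) through 6,060 (0.74) to 7,080 (0.81).

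**Step 4: simulation check.** An overlap-weighted Cox model with estimated propensity score and robust variance was simulated at about 7,600 per group, 600 replicates per scenario (Monte Carlo standard error about 2 points). Power was 78-81% with no separation, 72-76% at c = 0.63, 67-69% at 0.74 and 62-65% at 0.81. That agrees with the table or runs slightly below it.

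**Step 5: when the check misfires.** At 1:1, a comparison of head count with 7,600 gives the wrong answer only between 7,600 and the last column, roughly 8,050 to 10,750. At 12,000 per group with RE of 0.7 to 0.9, power is 82-90% (closed form), so passing is right.

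**The case against.** A reader might infer that the study is underpowered, or that the check will pass wrongly. The protocol supports neither. It gives no expected cohort size: 7,600 is a requirement, not planned enrolment, and index dates span six years at about 20 health systems. A cohort well above 10,750 per group, or one arm much larger than 7,600, would remove the problem. Nor does anything in the protocol show which c-statistic to expect, so 65-75% cannot be stated as the power of this study.

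Follow-up may also be longer than assumed. Index dates in 2015-2019 allow 24 months and those in 2020 allow 12 to 24. If initiations were uniform over the six years, the average would be (5 × 24 + 18)/6 = 23 months, against 18 in section 9.5. That is up to 28% more person-time, and at c = 0.74 it would more than offset the weighting loss (0.827 × 1.28 = 1.06). As-treated censoring pulls the other way by an unknown amount. This stands: the table isolates the effect of weighting at the protocol's stated follow-up and does not estimate net power.

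Section 9.7.1 uses observed aggregate event rates, so 7,600 is not a fixed pass mark there, and it leaves further detail to the SEAP, which is not at hand. That document may already use an effective sample size. But the protocol itself states the N, the power and the consequence of missing it. As worded, the figure belongs to a different analysis from the one it governs.

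**Conclusion.** The point holds in a limited form. The arithmetic of Table 4 is sound for the test it names, but 7,600 per group, and 5,000 in the higher-rate subgroup, are presented as sufficient for a primary analysis that extracts less information per patient. At the protocol's own rate and follow-up, with 7,600 in each group, power is below 80% whenever the propensity score varies. How far below is an assumption: about 78%, 72% and 65% at c-statistics of 0.63, 0.74 and 0.81, with about 8,050 to 10,750 per group needed to restore 80%. The checks in 9.1 and 9.7.1 can pass wrongly in a cohort modestly above 7,600 per group, and would not do so in a clearly larger one. This is worth correcting because the figure drives a stated decision and the correction is nearly free.

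**What to change.** In section 9.5, Table 4 and the Abstract, state that the required N is the effective sample size per group after overlap weighting.

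In sections 9.1 and 9.7.1, base the power check on the effective sample size per arm, (sum w)^2 / sum w^2. Compute it from the Phase 1 overlap weights, overall and within the DKD and non-DKD groups, and combine it with the observed aggregate as-treated event rate and follow-up. This replaces both the assumed propensity-score distribution and the assumed 18 months with observed values.

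Do not write 65-78% into the protocol as the study's power; it rests on a propensity-score distribution that the protocol does not give.

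The cost is wording in four places and one extra quantity per arm. Phase 1 already assesses balance after weighting, so the weights exist before any comparative outcome analysis, and no extra patients or outcome results by arm are needed. The downside is that the stated requirement becomes slightly less favourable.
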